Receipt of primary/preventive care, avoidance of non-recommended care, and PROs are secondary endpoints, and the analyses are descriptive. The analysis for receipt of primary/preventive care is similar to that for cancer-related follow-up. The endpoint for the avoidance of non-recommended care will be the proportion of patients who do not receive tests that are not recommended in the year following completion of acute treatment. This will be evaluated as a dichotomous variable (did not receive inappropriate care: yes vs. no). For the patient-reported outcomes, we will report the PRO scores by intervention arm at baseline, 6-month, 12-months, and 18-months. The main PRO analysis will be a comparison of the follow-up scores at 12-months by intervention arm adjusting for baseline. We will also compare the PROs at 6 months for Arms B&C vs. Arm A to evaluate the effective of the in-person transition visit vs. just sending the SCP. For the PLANS, we will report mean (SD) scores at the individual item level. For the ASC, we will primarily report the mean (SD) on the two subscale scores, but will also report the individual items and total score. For the FOCUS Information Needs, we will primarily report total number of health information needs (i.e., number of items endorsed “yes”), but will also report individual needs endorsed (dichotomous). For all of the PROs, we will also explore changes longitudinally using appropriate methods (GEE, random effects) and examine any differences in the trends over time between patient subgroups using interaction tests as needed.

d. Early stopping rules.

Early stopping rules are not applicable to this study.

8. Risks

a. Medical risks, listing all procedures, their major and minor risks and expected frequency.

There is a risk of participants feeling tired, bored, or uncomfortable when answering questions about health and health care.

b. Steps taken to minimize the risks.

Participants do not have to answer any question they do not want to answer.

c. Plan for reporting unanticipated problems or study deviations.

The study will undergo review and approval by the IRB at the Johns Hopkins School of Medicine. All JHCRN sites have agreed to use the review of the Johns Hopkins IRB. The IRB requirements are in full compliance with Federal Regulations regarding the protection of human subjects. All appropriate HIPAA procedures will be followed. Any participant concerns and/or complaints or study deviations will be reported to the IRB immediately.

d. Legal risks such as the risks that would be associated with breach of confidentiality.

There is a risk that patient information will be seen by someone who is not a member of the research team. We take precautions to keep information we collect safe, secure, and confidential. Information will be encrypted and grouped with other participants' information without any personal identifiers and will only be used for this study. Documents with any identifying information will be kept in a locked location that is only accessible to study team members. Electronic information will be protected by log-on identification and password protected computer procedures. All data will be presented in a grouped manner in reports

and publications so that no one participant can be identified. PHI will be retained to justify screen failures, and will be stored under the same secure conditions as all study-related data for the length of the trial.

e. Financial risks to the participants.

Participants randomized to either Arms B or C, will have one or two visits. These visits will be billed to their insurance, but the participant will be responsible for any out-of-pocket costs such as copays. The visits are billable to insurance because the study is comparing three standard-of-care approaches. In current practice, insurance is billed for patients who have these visits.

9. Benefits

a. Description of the probable benefits for the participant and for society.

There are no direct benefits from participation in this study; however, issues that are discussed may aid participants' understanding and experience of survivorship care. Also, this research may serve to help future adult cancer survivors receive quality survivorship care.

10. Payment and Remuneration

a. Detail compensation for participants including possible total compensation, proposed bonus, and any proposed reductions or penalties for not completing the protocol.

Participants will be paid up to \$125 for their time spent participating in this study (See Table 5). The table below shows the study activities for which they will be compensated and the dollar amount of compensation per activity. Compensation will be mailed shortly after each study activity, or provided in person, depending on the type of activity.

Table 5: Participant Compensation Schedule

Study Activity	Compensation for Time
Baseline – shortly following enrollment	\$25
Providing information 6 months after end of treatment	\$25
Providing information 12 months after end of treatment	\$25
Providing information 18 months after end of treatment	\$25
Incentive for completing all 4 data points	\$25
TOTAL COMPENSATION AFTER COMPLETING ENTIRE STUDY	\$125

11. Costs

a. Detail costs of study procedure(s) or drug (s) or substance(s) to participants and identify who will pay for them.

Participants randomized to either Arms B or C, will have one or two visits. These visits will be billed to their insurance, but the participant will be responsible for any out-of-pocket costs such as copays.

References

American College of Surgeons Commission on Cancer. (2016). *Cancer program standards: ensuring patient-centered care, 2016 edition*. Available at <https://www.facs.org/quality-programs/cancer/coc/standards>.

Beckjord, E. B., Arora, N. K., McLaughlin, W., Oakley-Girvan, I., Hamilton, A. S., & Hesse, B. W. (2008). Health-related information needs in a large and diverse sample of adult cancer survivors: implications for cancer care. *Journal of Cancer Survivorship*, 2(3), 179-189.

Cohen, J. W., Monheit, A. C., Beauregard, K. M., Cohen, S. B., Lefkowitz, D. C., Potter, D. E. B., ... & Arnett III, R. H. (1996). The Medical Expenditure Panel Survey: a national health information resource. *Inquiry*, 373-389.

Gotay, C. C., & Pagano, I. S. (2007). Assessment of Survivor Concerns (ASC): a newly proposed brief questionnaire. *Health and quality of life outcomes*, 5(1), 1.

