OBJECTIVE: The purpose of this study is to identify an SCP process that is patient-centered, effective in promoting appropriate survivorship care and can be successfully implemented for patients with different types of cancer who are being treated in a broad range of clinical settings. There is a need for research related to SCP that prioritizes outcomes that are most highly valued by patients, caregivers and clinical stakeholders.

METHODS: In Year 1, we have worked with clinical partners and our Stakeholder Advisory Board, which consists of survivors, caregivers, members of the oncology team and primary care providers, to refine the three SCP approaches that will be tested in this trial. In addition, we conducted 6 focus groups (under IRB approval from the Johns Hopkins Bloomberg School of Public Health IRB #6805), four with patients and two with caregivers, to solicit patient and caregiver perspectives on the content, timing and delivery of survivorship care planning. We will now conduct a randomized controlled trial (RCT) to compare the impact of three models of varying intensity for SCP implementation, each of which is consistent with

current care practices. We will collect both quantitative (included here) and qualitative (to be added through a later amendment) assessments of the three SCP models.

2. Objectives (include all primary and secondary objectives)

The research is organized around three aims as outlined below:

AIM 1: Compare patients' receipt of follow-up care across the three models of SCP provision.

We will evaluate the effectiveness of three SCP models in facilitating patients' receipt of recommended health services in the 18 months following their completion of acute treatment. We will measure whether the mechanism of provision of the SCP to the patient is associated with their receipt of cancer-related follow-up care as outlined on their SCP (primary outcome). Secondary outcomes include avoidance of services that are not recommended and receipt of primary and preventive care.

AIM 2: Compare patient-reported outcomes across the three models of SCP provision.

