records, as well as from patient reports of health service use; data will be collected at months 6, 12, and 18. We will obtain and abstract medical records guided by the information in the summary document (see Health Services Use Summary included as a supplemental study document) and from the patient using provided tracking tools of providers they have seen, tests they have undergone, etc. (see Tip Sheet in supplemental study documents). Patient-reported outcomes will be collected at baseline, 6, 12, and 18 months primarily via a REDCap form, with telephone, mail, or in-person data collection as a back-up when needed (See Pro Data Collection form in supplemental study documents).

ARM A (SCP document delivered to the patient & Primary Care Provider [PCP]):

Patient participants randomized to Arm A will be sent a copy of the SCP within approximately 3 months of completion of treatment and a copy will be added to their medical record. A copy of the SCP will also be sent to the PCP on record. The SCP will be completed by a nurse, nurse practitioner, or physician assistant. The SCP will be accompanied by a cover letter that will be signed by a member of the clinical team.

ARM B (SCP document provided to the patient in an in-person survivorship visit and copy sent to PCP):

Patient participants randomized to Arm B will receive a copy of the SCP during an in-person ‘stethoscope free’ visit with a nurse, nurse practitioner, or physician assistant. A copy of the SCP will be added to the medical record and a copy will be sent to the primary care provider on record. The visit will be scheduled after consent is signed and will occur within approximately 3 months after treatment completion. The visit will focus on review of the SCP content and offer an opportunity for patients to ask questions about any aspect of the plan or associated treatment and survivorship issues.

ARM C (SCP document provided to the patient in an in-person survivorship visit with an additional follow-up visit and copy of the document sent to PCP):

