We will follow participants for 18 months or until cancer recurrence, at which point they would not receive any further survivorship care planning visits, and no additional health service use or patient reported outcomes data would be collected. Treatment failure is not relevant to this study, and we will not remove participants unless they explicitly withdraw consent. Even if patients do not complete the follow-up surveys, we can still collect their health resource use from their medical records (unless they have withdrawn consent).

g. Description of what happens to participants receiving therapy when study ends or if a participant's participation in the study ends prematurely.

Not applicable as no therapy is included in this study.

RECRUITMENT PROCESS: Clinic and study staff trained in research ethics and HIPAA requirements will coordinate identification and recruitment of potential participants. Specifically, potential participants will be identified during chart review in advance of a routine clinic visit or during a routine clinic visit with a provider. The research team will be searching medical records for patients who have completed, or will soon be completing, treatment. Searching for patients with active treatment appointments is one, but not the only, way we may identify eligible patients. The clinical teams have agreed to provide us with insights on the best ways to identify patients potentially eligible for the study based on their medical records. Potential participants will be approached by a member of clinic staff to determine willingness to learn more about a study for which they may be eligible.

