Outcome Measures (Based on NCCN 2013 and ASCO Guidelines)					
TUMOR TYPE	BREAST	COLORECTAL	PROSTATE	Data Collection Timing and Approach	
Stage	Stage I-III	Stage I-III	Stage I-III		
HEALTH SERVICE USE	Recommended Surveillance	Every 3-6 months: H&P exam Annually: Mammography (excluding women with bilateral mastectomy)	Every 3-6 months: H&P exam CEA Annually: CT scan chest, abdomen, and pelvis Colonoscopy (ok to do first at year 3 if preoperative full colonoscopy normal)	Every 6-12 months: H&P exam PSA	
Patient reports assessed at: Baseline & Months 6, 12, 18
 
Medical records abstracted at: Month 18
 
All health service use variables will be based on medical record abstractions, guided by patient tracking tools. During the study contacts, we will obtain patients' reports of providers they have seen, tests they have undergone, etc. At Month 18, we will obtain & abstract all relevant medical records.

	Not Recommended Surveillance (assumes normal H&P and normal recommended surveillance)	Imaging Breast MRI FDG PET/CT CT chest, abdomen, pelvis Liver ultrasound Bone scan Blood tests Tumor marker CEA, CA15-3, or CA27-29	Imaging Chest X-ray FDG PET/CT	Imaging FDG PET/CT Bone scan	
	Recommended Preventive Care Measures	Visit with primary care provider Annual influenza immunization			

The general recommendations will be based on Table 1, but the clinician completing the form can tailor the specific recommendations based on clinical judgement. As described above, the SCP will either be sent to the patient (Arm A) or delivered in an in-person visit conducted by a nurse, nurse practitioner, or physician assistant (Arms B & C).

For all arms, participants will be followed for 18 months, or until cancer recurrence. The participants will be contacted approximately 6, 12, and 18 months after the end of treatment to provide data on health service use and patient-reported outcomes.

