Health service use will be collected from patient-report via telephone or in-person at 6, 12, and 18 months after completion of treatment, as well as from medical records. Patients will be supplied with a calendar and asked to note office visits, hospitalizations, emergency department visits, prescriptions, tests, and other health resource use. We will also provide participants with a tip sheet for tracking providers visited, care received, tests done, and prescriptions obtained. The tip sheet template has been adapted from the Medical Expenditure Panel Survey, courtesy of the Agency for Healthcare Research & Quality (see study supplemental documents) (Cohen, et al., 1996). At each data collection point, patients will use these resources to report what health services they have received during the past 6 months.

We will also request and abstract the medical record of each participant for the 18-month study period. The abstraction will focus specifically on surveillance and preventive care. We will also collect all health service use during the study period (outpatient visits, tests, imaging studies, hospitalizations, emergency department visits, medication list). These data will allow us to explore receipt of other preventive and screening services that may be age-based and/or not required on an annual basis (e.g., cholesterol screening, cervical cancer screening), as well as overall health service use (see supplemental study documents for Health Services Use document) .

Patient-reported outcomes will be collected at baseline, 6, 12, and 18 months. The default mechanism for these contacts will be via a REDcap form, with a link sent to the participants via email (see supplemental study documents for Pro Data Collection form). Where this is not possible, the research staff will collect data on the telephone, by mail or in-person.

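### The health-service windows open at the end of treatment, not at randomisation, so services used before randomisation can enter the endpoints, most clearly the avoidance endpoint

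*Combined protocol and SAP*

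**What the plan says.** **Window.** Section 2, Aim 1, evaluates "receipt of recommended health services in the 18 months following their completion of acute treatment". Section 4 (Study Implementation) uses the same clock: participants are "contacted approximately 6, 12, and 18 months after the end of treatment", and health service use is collected at "6, 12, and 18 months after completion of treatment, as well as from medical records". At each contact patients "report what health services they have received during the past 6 months", so the month-6 report reaches back to the end of treatment. The team will also "abstract the medical record of each participant for the 18-month study period"; no start date is given at that point. Section 7c (Data Analysis) defines the avoidance endpoint over the year after acute treatment is completed.

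**Entry.** Section 4 (Recruitment Process) states: "The research team will be searching medical records for patients who have completed, or will soon be completing, treatment". The Section 5 criteria set no maximum time from the end of treatment to enrolment. Arm A patients "will be sent a copy of the SCP within approximately 3 months of completion of treatment". In Arms B and C the first visit is scheduled after consent and has the same target of about 3 months.

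**Scoring.** Section 7a scores the primary endpoint yes/no against the individual's SCP, and Section 7c requires all cancer-related follow-up care to have been received. Avoidance and primary/preventive care are also yes/no. No rule excludes services used before randomisation.

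**The concern.** The trial asks whether the way an SCP is delivered changes the care that patients then receive. Events before randomisation cannot depend on the arm. If the scored window opens earlier, part of each yes/no outcome may be settled before the intervention can act. A non-recommended test already done is a permanent failure, and a recommended service already obtained is a success that no arm had to earn. Both pull the arms together.

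This matters because the primary endpoint is to decide which delivery model is preferable, and the study is looking for the least demanding approach that works. An attenuated difference would make the least intensive arm look adequate more often than it should. Abstractors also need a stated rule for services dated before randomisation if the endpoints are to be reproducible.

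**Working it through.** **1. Share of each window that precedes randomisation.** Let m be the month of randomisation counted from the end of treatment. The share is m/12 for avoidance (Section 7c) and m/18 for the other endpoints (Section 2). The documents give no distribution of m. The range shown is assumed, with month 3 taken from the SCP delivery target.

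| m (assumed) | Avoidance, m/12 | 18-month endpoints, m/18 |
|---|---|---|
| 0 or earlier | 0% | 0% |
| 1 | 8.3% | 5.6% |
| 2 | 16.7% | 11.1% |
| 3 | 25.0% | 16.7% |

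**2. Avoidance.** No due date is needed: one listed test inside the window is a failure. If a share q of patients in every arm has such a test before randomisation, an arm rate p becomes p(1 − q), and every difference is multiplied by (1 − q). With assumed q of 5, 10 or 20%, a 15-point difference becomes 15 × 0.95 = 14.25, 15 × 0.90 = 13.5 or 15 × 0.80 = 12 points.

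**3. Care already received.** If a share r has the deciding item credited before randomisation, p becomes r + (1 − r)p and the difference is multiplied by (1 − r). This is the single-item case. With several required items, the effect depends on which are credited. Candidates in Table 1 are the annual tests, the influenza immunisation and the primary care visit.

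**4. Missed primary-endpoint items.** Due dates from Table 1, counted from the end of treatment:

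- Every 3 months (shortest breast and colorectal interval): 3, 6, 9, 12, 15, 18. None is before month 3; one is at month 3.
- Every 6 months: 6, 12, 18. None is before month 3.
- Every 12 months: 12. None is before month 3.

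The breast and colorectal interval is 3 to 6 months, so a patient not yet seen at month 3 can still be on schedule. On these dates q is about 0.

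**5. What a loss would cost, if there were one.** Exact power of the three-arm Fisher test (two-sided 0.05, 125 per arm), by full enumeration, gives 79.4% for rates 30/39.5/49%, against 79.2% in Table 3. All 18 rows of Table 3 reproduce within 2 points. Treating the Table 3 rates as rates on care after randomisation and applying p(1 − q):

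| Rates A/B/C | q = 0 | 5% | 10% | 20% |
|---|---|---|---|---|
| 30/39.5/49% | 79.4% | 75.7% | 71.8% | 63.3% |
| 50/55/70% | 86.5% | 81.6% | 76.3% | 65.0% |
| 70/75/87.5% | 89.9% | 81.3% | 71.9% | 54.9% |

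In the first row the A–C difference goes from 19.0 to 18.1, 17.1 and 15.2 points. With early credit as in step 3 and r of 5, 10 or 20%, first-row power is 73.6, 67.8 or 56.4%. The values of q and r are assumptions; the documents supply neither.

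**The case against.** A reader might infer something stronger: that care due before randomisation is counted in the primary endpoint and dilutes every contrast by a sizeable amount. One calculation supporting that view spreads misses evenly over 18 months and randomises everyone at month 3. Early adherence is then 0.50^(3/18) = 0.891, and rates of 50% and 65% correspond to 0.50/0.891 = 56.1% and 0.65/0.891 = 73.0% on later care. A difference of about 17 points is seen as 15, a loss of about 11%. Starting from 30% and 45%, early adherence is 0.818, the later rates are 36.7% and 55.0%, and the loss is about 18%.

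The documents do not support that reading:

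- The primary endpoint is scored against the individual's SCP, which Section 3 describes as setting out care needed from then on. Nowhere is it said that items due earlier are scored.
- Even spreading contradicts the discrete intervals in Table 1, which put nothing before month 3. An earlier miss would need a shorter tailored interval, a clock starting before the end of treatment, or later enrolment. None of these is shown.
- Recruitment covers "patients who have completed, or will soon be completing, treatment", so some patients have no time before randomisation in the window. Prostate patients, 150 of the 375 planned, are on 6- to 12-month intervals.

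Nor is there bias between arms: events before randomisation are balanced in expectation. A common anchor at treatment completion is also a legitimate choice for a study of care transition, and the baseline patient report listed in Table 1 may help to separate earlier use.

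These arguments dispose of the strong claim for missed primary items. They do not answer the avoidance endpoint, whose window Section 7c ties explicitly to treatment completion, or the crediting of care already received.

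**Conclusion.** The point holds in limited form. Followed as written, the windows open at the end of treatment, and patients may be randomised later, so services used before randomisation can count. Avoidance is most exposed: up to 25% of its window for a patient randomised at month 3, and nothing for a patient randomised by the end of treatment. Early credit for recommended or preventive care works in the same direction. For missed primary items the effect may be near zero.

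No overall loss can be stated without the distribution of enrolment times and the rates of early testing and early care. The power figures for 5 to 20% show sensitivity and are not estimates for this trial. The consequence is attenuation and lost power. For avoidance and preventive care, which Section 7c calls descriptive, that means smaller reported differences and not the failure of a powered test. The correction is worth making because it is cheap and removes an ambiguity in scoring.

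**What to change.** Apply one rule in all arms:

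- **Avoidance:** count only non-recommended tests done after randomisation, ending one year after treatment completion, as Section 7c already states. Do not extend this window to month 18.
- **Primary and preventive care:** score items falling due after randomisation, up to month 18 after treatment completion. State how an annual service obtained shortly before randomisation is handled.
- **Start date:** use randomisation, not SCP receipt. Receipt comes after randomisation and can differ by arm.
- **Sensitivity analysis:** report the windows from treatment end alongside, with the distribution of time from treatment end to randomisation by arm.

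The cost is mainly wording, provided that the abstraction form, a supplement not included here, records service dates; this should be confirmed. The scored window becomes slightly shorter and varies between patients. For randomisation at month 3 it is 12 − 3 = 9 months for avoidance and 18 − 3 = 15 months otherwise. The distribution of lengths is expected to be the same in every arm. The rule does not remove the wait between randomisation and SCP delivery, which belongs to the comparison of models as randomised.
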